2.4 Effectiveness analysis

2.4.1 Datasets analyzed

[figure not shown]
All effectiveness variables will be analyzed using the FAS population. The primary analysis will be repeated using the PP population. If it is deemed necessary, other analyses will be repeated using the PP population.

2.4.2 Handling of missing data

Number of missing values will be summarized and reported as appropriate. The baseline observation carried forward (BOCF) method will be used as the primary method to handle missing data on the primary effectiveness variable at the Month 6 visit in the FAS analysis set. This strategy is a conservative approach as it treats subjects with missing data as non-responders. Impact of missing data on the primary analysis for Month 6 endpoint will be evaluated by performing sensitivity analysis based on the PP population. In addition, missing data for the primary analysis will also be handled using the hot deck method.

All other endpoints will be analyzed on available data, i.e. no imputations will be done.

CCI

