1.1.2 Number of subjects and randomization

Approximately 148 subjects will be randomized in a 3:1 ratio to treatment with Restylane Defyne or to no-treatment Control Group. The randomization will be stratified by center.

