2.1 General methods

All statistical analyses, including summary tables and data listings, will be performed using the SAS® system (version 9.4 or later).

In general, effectiveness, safety, demography, subject characteristics, and treatment related variables will be presented using descriptive statistics. Continuous data will be summarized using n (number of observations), mean, standard deviation, median, minimum and maximum value, while categorical data will be presented by frequency and percentage. Graphs may be used as appropriate.

All statistical testing will be two-sided and performed at a significance level of 5%. Confidence intervals will be 2-sided and constructed using 95% confidence level.

Any change made to the finalized statistical analysis plan (SAP) will be documented in the Clinical Study Report (CSR).

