2.4.3 Primary effectiveness analysis

The responder rate will be calculated for each group at Month 6 (after last treatment in Treatment Group and after randomization in Control group) based on the blinded evaluator's assessment. The responder rate in the Treatment Group will then be compared with the responder rate in the Control Group using a Fisher's exact test at a significance level of 5%. In addition, for each group the two-sided 95% confidence interval around the estimates of the percentage of responders will also be calculated. The treatment will be deemed a success if the p-value for the treatment difference on the primary endpoint is less than 0.05.

In order to assess robustness of the conclusions of the primary endpoint analysis, a logistic regression will be utilized, including baseline GCRS and treatment group as factors. The overall treatment effect will be used for assessing the robustness of the result of the primary analysis when corrected for baseline GCRS.

In addition, to obtain an estimate of the true clinical treatment effect, the primary analysis will be re-run using the PP analysis set.

 GALDERMA	Title Statistical Analysis Plan 43CH1627 - Chin	Doc id MA-38115
--	---	---------------------------

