2.7 Determination of Sample Size

CCI

CCI

To account for 15% dropouts, approximately 111 will be randomized to the Restylane Defyne Treatment Group and approximately 37 to the Control group.

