**Table A 17. GCRS responder rate by treatment at Month 6, Blinded Evaluator (FAS)**

Time point	Treatment group	# of subjects in FAS	# of responders	Proportion of responders	95% confidence interval	P-value
6 month after last treatment	Restylane Defyne	xx	xx	x.xx	x.xx, x.xx	
6 month after randomization	Control	xx	xx	x.xx	x.xx, x.xx	
Difference	-			x.xx	x.xx, x.xx	x.xx

Note: Subjects with a missing GCRS have their values imputed using BOCF at Month 6

Note: Responder is defined as a subject with an improvement of at least one grade on the GCRS from baseline

Note: Responder rate is calculated as the number of Responders divided by the number of subjects in the FAS population for the specific treatment group.

Note: P-values for the difference in proportions are based on the Fisher's Exact test

Note: 95% Confidence Intervals are two-sided and calculated using the binomial distribution

Table A 18. GCRS responder rate by treatment at Month 6, Blinded Evaluator (PP)

As Table A 17.

Note: No imputation is used for the PP analysis. Only subjects with complete data are included.

Note: Responder is defined as a subject with an improvement of at least one grade on the GCRS from baseline

Note: Responder rate is calculated as the number of Responders divided by the number of subjects in the FAS population for the specific treatment group.

Note: P-values for the difference in proportions are based on the Fisher's Exact test

Note: 95% Confidence Intervals are two-sided and calculated using the binomial distribution

Table A 19. Sensitivity analysis for the GCRS responder rate by treatment at Month 6, Blinded Evaluator (FAS)

As Table A 17.

Note: Subjects with a missing GCRS have their values imputed using the hot deck method at Month 6

Note: Responder is defined as a subject with an improvement of at least one grade on the GCRS from baseline

Note: Responder rate is calculated as the number of Responders divided by the number of subjects in the FAS population for the specific treatment group.

Note: P-values for the difference in proportions are based on the Fisher's Exact test

Note: 95% Confidence Intervals are two-sided and calculated using the binomial distribution

Table A 20. Logistic regression, Blinded Evaluator (FAS)

Parameter	Coefficient	SE	Wald Chi-Square	Degrees of freedom	P-value
Baseline GCRS	x.xx	x.xx	x.xx	x	x.xx
Treatment Group	x.xx	x.xx	x.xx	x	x.xx

Title

Statistical Analysis Plan 43CH1627 - Chin

Doc id

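### Table A 19 appears to analyse a single hot deck data set as if every value had been observed, so this sensitivity analysis overstates its precision

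*SAP*

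**What the plan says.** SAP 2.4.2 makes BOCF the main approach to a missing Month 6 blinded GCRS ("The baseline observation carried forward (BOCF) method will be used as the primary method") and adds that "missing data for the primary analysis will also be handled using the hot deck method". Protocol 10.6 gives the reasoning: BOCF treats missingness as lack of effect, and an alternative analysis treats it as unrelated to the treatment effect. Both are meant to estimate the treatment policy effect.

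The hot deck results go into Table A 19, which refers back to Table A 17 for its layout. Its notes state that "Subjects with a missing GCRS have their values imputed using the hot deck method at Month 6" and that "P-values for the difference in proportions are based on the Fisher's Exact test". They take all FAS subjects in the arm as the denominator and compute the 95% intervals from the binomial distribution.

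The visible text gives no donor class, number of imputations, pooling rule, variance correction or seed. Redacted text follows the missing-data wording in both SAP 2.4.2 and protocol 10.6 and may hold some of these.

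Success is defined in SAP 2.4.3: "The treatment will be deemed a success if the p-value for the treatment difference on the primary endpoint is less than 0.05".

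**The concern.** A hot deck value is a copy of another subject's outcome and carries no new information. It also adds the noise of the random donor draw. An analysis that divides by the full FAS count and applies Fisher's test or a binomial interval ignores both facts, so its standard error is too small.

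This matters because Table A 19 is the only visible analysis that keeps every FAS subject and relaxes BOCF. The PP analysis excludes subjects without the Month 6 blinded score (SAP Table 3) and imputes nothing. The logistic regression adjusts for baseline GCRS and does not address missing data. If Table A 19 looks more precise than it is, it can support a claim of robustness that the data do not justify. A single random draw also makes the result depend on the seed.

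**Working it through.** **Inputs.** The significance level is 5%, two-sided (SAP 2.1). On size, SAP 1.1.2 says "Approximately 148 subjects will be randomized in a 3:1 ratio to treatment with Restylane Defyne or to no-treatment Control Group", and SAP 2.7 says "To account for 15% dropouts, approximately 111 will be randomized to the Restylane Defyne Treatment Group and approximately 37 to the Control group". The planning response rates, power and evaluable N are redacted, so all response rates below are assumptions shown over a range.

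**The plan's own figure.** 111 + 37 = 148 and 111/37 = 3. Fifteen percent missing is 0.15 × 111 = 16.65, so 17 subjects, and 0.15 × 37 = 5.55, so 6 subjects. That leaves 94 and 31 observed. Inflating back, 94/0.85 = 110.6 and 31/0.85 = 36.5, which round to 111 and 37. The power calculation cannot be reproduced.

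**Step 1: standard error, donors from the same arm.** Let n be the FAS count in an arm, r the number observed and m = n − r. With random donors drawn with replacement and data missing completely at random, the variance of the filled-in responder rate, relative to the assumed p(1−p)/n, is

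n/r + (m/n)(1 − 1/r).

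- Treatment: 111/94 + (17/111)(1 − 1/94) = 1.181 + 0.152 = 1.332; square root 1.154.
- Control: 37/31 + (6/37)(1 − 1/31) = 1.194 + 0.157 = 1.350; square root 1.162.

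**Step 2: Fisher's test, donors from the same arm.** The filled-in count is the observed count X plus a Binomial(m, X/r) draw. Exact enumeration under equal true rates, 15% missing, gives these type I errors:

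| Common rate | Filled-in data | Full data | Complete cases |
|---|---|---|---|
| 5% | 4.9% | 2.6% | 2.4% |
| 10% | 6.7% | 3.5% | 3.1% |
| 20% | 7.4% | 3.8% | 3.5% |
| 30% | 7.7% | 3.9% | 3.8% |
| 50% | 7.1% | 3.6% | 3.8% |

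Over the same rates, the filled-in analysis rejects 3.4–5.1% at 5% missing (up to about 5.5% by simulation), 4.1–6.3% at 10% and 5.5–8.5% at 20%.

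**Step 3: per-arm intervals.** Exact binomial (Clopper-Pearson) coverage at 15% missing is 92.8–94.8% in the treatment arm (rates 50–90%), against 96.2–97.5% with full data. In the control arm (rates 5–50%) it is 91.1–97.6%, against 95.3–99.0%.

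**Illustration.** Observed counts of 56/94 and 12/31 give Fisher p = 0.061. Filled in at nearly the same rates, 66/111 and 14/37 give p = 0.035. Nothing was learned, yet the result crosses 0.05.

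**Step 4: donors pooled across arms.** Simulated Fisher type I error at 15% missing is about 3–4%, so it is not inflated. The estimate is biased instead. With true rates of 70% and 20%, the donor rate is (94 × 0.70 + 31 × 0.20)/125 = 0.576. The filled-in rates are (65.8 + 17 × 0.576)/111 = 0.681 and (6.2 + 6 × 0.576)/37 = 0.261, so a true difference of 0.50 becomes 0.42. Interval coverage in this case is 91.6% and 85.8%.

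**Step 5: the remedy, 15% missing.** Within-arm multiple hot deck (approximate Bayesian bootstrap, 50 imputations, Rubin's rules) gives Wald coverage of the difference of 93.2–93.8%. A single hot deck gives 89.0–89.8% and complete cases 93.1–94.0%. Mean width at 70% against 20% is 0.330 rather than 0.302, and 0.330/0.302 = 1.09. The choice of test matters. An unpooled Wald p-value with Rubin's rules rejects about 15% at a common rate of 5%, about 8% at 10% and 6–7% at 20–50%. A score-type test, which adds the between-imputation variance to a null-pooled variance, rejects about 3–6%.

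**The case against.** Four objections carry weight.

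1. The donor rule is not visible. A reader might infer that the hot deck test certainly exceeds 5%. The documents do not support that, because the excess disappears if donors are pooled across arms.
2. Table A 19 is a mock shell. Its notes are copied, and the same notes misfit elsewhere: Table A 18 keeps an FAS denominator for the PP set, and in Table A 22 the column heading and the note disagree on the denominator. A reader might infer that pooling over repeated draws is ruled out. The shell makes a single data set the likely reading, but it does not exclude redacted detail.
3. The 15% is a dropout allowance for sample size, not a forecast of missing Month 6 scores in a study lasting 14 to 20 months. At 5% missing, Fisher's conservatism absorbs most of the effect.
4. No decision rests on this table. A reader might infer that the trial's conclusion is at risk, but the success rule refers to the primary endpoint, for which BOCF is the primary method. With a large effect the hot deck result would not change either: power exceeds 99% at 60% against 10% or 70% against 20%.

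These points limit the size and certainty of the concern. They do not remove it. The stated test, interval and denominator treat imputed values as observed, and either donor rule leaves a fault in the reported results.

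**Conclusion.** The concern holds for this sensitivity analysis, read as its shell is laid out. With within-arm donors and 15% missing, the SE is understated by a factor of about 1.15 and Fisher's type I error is about 5–8%, roughly double the complete-case figure. With pooled donors the fault becomes bias toward zero, and the per-arm intervals still mostly under-cover. These sizes rest on data missing completely at random, random donors drawn with replacement, assumed response rates, and a missing fraction near the sample-size allowance. The BOCF primary test and the success rule stand. This should be corrected before database lock because the repair is cheap, but it does not threaten the main conclusion.

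**What to change.** In SAP 2.4.2, state that donors are drawn within treatment arm and baseline GCRS. Specify multiple hot deck imputation by approximate Bayesian bootstrap, with at least 50 imputations and a fixed seed. The figures above use arm alone as the donor class.

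In Table A 19, replace the Table A 17 layout with the responder rate in each arm and the difference, each with a Rubin-pooled 95% interval. Do not put an unpooled Wald p-value in place of Fisher's. Either pool a score-type test (null-pooled variance plus between-imputation variance), or drop the p-value and label the table descriptive.

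The cost is a few sentences in the SAP, a revised shell, minor programming, and intervals about 9% wider at 15% missing.

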2.4.3 Primary effectiveness analysis

The responder rate will be calculated for each group at Month 6 (after last treatment in Treatment Group and after randomization in Control group) based on the blinded evaluator's assessment. The responder rate in the Treatment Group will then be compared with the responder rate in the Control Group using a Fisher's exact test at a significance level of 5%. In addition, for each group the two-sided 95% confidence interval around the estimates of the percentage of responders will also be calculated. The treatment will be deemed a success if the p-value for the treatment difference on the primary endpoint is less than 0.05.

In order to assess robustness of the conclusions of the primary endpoint analysis, a logistic regression will be utilized, including baseline GCRS and treatment group as factors. The overall treatment effect will be used for assessing the robustness of the result of the primary analysis when corrected for baseline GCRS.

In addition, to obtain an estimate of the true clinical treatment effect, the primary analysis will be re-run using the PP analysis set.

 GALDERMA	Title Statistical Analysis Plan 43CH1627 - Chin	Doc id MA-38115
--	---	---------------------------

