4.4 Randomization and blinding

4.4.1 Randomization

Approximately 148 subjects will be randomized in a 3:1 ratio to treatment with Restylane Defyne or to no treatment. Before starting the study, a computer generated randomization list will be prepared under the supervision of a designated statistician. The randomization list will be stratified by center.

Each subject will be assigned a subject number as they arrive for the treatment visit. Randomization will be assigned via the eCRF system. The treatment information will be kept by the Treating Investigator during the study not to be disclosed to the Blinded Evaluator.

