10.6 Handling of Missing Data

Number of missing values will be summarized and reported as appropriate.

Different assumptions regarding the missing data will be used. For the primary effectiveness analysis, missing values in the FAS will be assumed to be missing due to lack of effect. Therefore missing data up to the Month 6 visit will be imputed using the baseline observation carried forward (BOCF) method. As an alternative approach, missing data will be assumed to be unrelated to treatment effect. CCI

More details will be given in the SAP. Both of these alternatives will estimate the effectiveness of the treatment policy (irrespective of use of unallowable treatments, procedures, or medications) rather than the true, clinical treatment effect.

To obtain an estimate of the true clinical treatment effect, the primary effectiveness analysis will be performed using the PP.

All other endpoints will be analysed on available data, i.e. no imputations will be done.

| | | |
|--|--|---------------------------|
|  GALDERMA | Title 43CH1627 Clinical Study Protocol | Doc id MA-34970 |
|--|--|---------------------------|

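### If no control subject responds, the treatment test in Table A 20 has no usable result and no fallback is named; center, the only stated stratification factor, is in neither Month 6 analysis

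*SAP*

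**What the plan says.** The primary analysis in SAP 2.4.3 is unstratified: "The responder rate in the Treatment Group will then be compared with the responder rate in the Control Group using a Fisher's exact test". The two-sided level is 5%, and success is defined by that p-value alone.

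The same section adds a robustness model: "a logistic regression will be utilized, including baseline GCRS and treatment group as factors". Its purpose is stated: "The overall treatment effect will be used for assessing the robustness of the result of the primary analysis", corrected for baseline GCRS. The shell of Table A 20 has a coefficient, a standard error, a "Wald Chi-Square" column, degrees of freedom and a p-value, with one row for baseline GCRS and one for treatment. It has no likelihood-ratio, exact or penalized column and no note on non-convergence.

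Missing Month 6 values are set to baseline, and SAP 2.4.2 notes that "it treats subjects with missing data as non-responders". Protocol 10.6 gives the reason: "missing values in the FAS will be assumed to be missing due to lack of effect".

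On stratification, protocol 4.4.1 says "The randomization list will be stratified by center" and SAP 1.1.2 says "The randomization will be stratified by center". No other factor is stated. In the visible text, site is used only for subject counts and listings (SAP 2.3.1, Tables A 2 and A 5).

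**The concern.** There are two independent points, and one change to Table A 20 can deal with both.

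**Separation.** Controls are untreated until after the Month 6 assessment, only 37 are planned, and a missing control counts as a non-responder. Zero control responders is therefore a plausible result. It would be quasi-complete separation: the likelihood keeps rising as the treatment coefficient grows, so no finite estimate exists. The standard error grows faster than the coefficient, and the Wald statistic falls to zero. The robustness check would then print a clearly non-significant treatment effect beside a decisive primary result, and so fail where the evidence is strongest. A substitute fit could be documented in the study report under SAP 2.1, but it would be chosen after the data were seen.

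**Center.** The randomization is balanced within center, but neither the primary test nor the supporting model uses center. This does not threaten Fisher's validity. It can cost power, and it leaves the only adjusted analysis not reflecting the design.

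**Working it through.** **Inputs from the documents.** 148 subjects at 3:1, 111 and 37 per arm, 15% dropout (SAP 1.1.2 and 2.7); about 5 centers (protocol 4.2); baseline GCRS 1 or 2 (protocol 5.2).

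**The plan's own figure.** 148 × 3/4 = 111 and 148 × 1/4 = 37. Allowing for dropout, 94/0.85 = 110.6 and 31/0.85 = 36.5, which round up to 111 and 37. The assumed response rates and power are redacted, so the sample size itself cannot be reproduced. Nothing below depends on it, but control rates have to be assumed.

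**Step 1: how the Wald test fails.** Illustrative data: 78/111 treated responders (36/55 at GCRS 1, 42/56 at GCRS 2) and 0/37 controls. Newton-Raphson fit with intercept, baseline GCRS and treatment:

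| Iteration | Coefficient | SE | Wald chi-square | p |
|---|---|---|---|---|
| 5 | 7.09 | 3.65 | 3.78 | 0.052 |
| 8 | 10.10 | 16.31 | 0.383 | 0.54 |
| 12 | 14.10 | 120.5 | 0.014 | 0.91 |
| 20 | 22.10 | 6,581 | 0.00001 | 0.997 |

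Between iterations 8 and 12 the coefficient rises by 1 per step, while the SE is multiplied by (120.54/16.31)^(1/4) = 1.65 per step. The printed p-value therefore reflects the stopping rule, not the data. On the same data Fisher p = 1e-15, the likelihood-ratio chi-square is 70.2 (p = 5e-17) and the Firth penalized likelihood-ratio chi-square is 65.6 (p = 5e-16). Only the treatment row fails; the baseline row stays estimable from the treated arm. With 1/37 control responders the fit converges (4.49, SE 1.04, Wald 18.7).

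**Step 2: two further examples.** The baseline split is assumed to be 50/61 treated and 17/20 control, with subjects allocated at random to 5 centers.

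| Data | Fisher p | ML Wald p, iterations 8 to 20 | Firth with center, penalized LR p | CMH by center p |
|---|---|---|---|---|
| 83/111 v 0/37 | 2e-17 | 0.53 to 0.997 | 2e-17 | 4e-15 |
| 30/111 v 0/37 | 8e-5 | 0.62 to 0.998 | 5e-5 | 4e-4 |

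Adding center by ordinary maximum likelihood does not help in the larger example (0.52 to 0.997). With 83/111 v 1/37 the ML Wald p is 7e-6.

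**Step 3: chance of zero control responders.** With true control rate p it is (1 − p)^37. With 15% missing and counted as non-responders it is (1 − 0.85p)^37.

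| p | 1% | 2% | 5% | 10% | 15% | 20% |
|---|---|---|---|---|---|---|
| No missing data | 69% | 47% | 15% | 2% | 0.2% | 0.03% |
| 15% missing | 73% | 53% | 20% | 4% | 0.6% | 0.1% |

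**Step 4: chance of a contradiction.** All outcomes for 111 v 37 were enumerated (treatment-only model, a zero cell counted as Wald p = 1). The probability that Fisher p < 0.05 while Wald p ≥ 0.05 is 69%, 47%, 15% and 2% at control rates of 1%, 2%, 5% and 10% when the treated rate is 50% or 75%. At a treated rate of 30% it is 69%, 48%, 16% and 4%. Nearly all of it comes from zero control responders.

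**Step 5: center.** Fisher's size under no effect was simulated with 3:1 allocation fixed within five centers (20,000 runs each). It was 3.4% with all centers at 10%, 4.1% with all at 30%, 2.5% with centers from 0 to 40%, and 0.7% with centers from 5 to 90%. It never exceeded 5%.

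Power at 45% v 20% (100,000 replicates; center effect normal on the logit scale and common to both arms; near-equal centers):

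| Between-center SD (assumed) | Fisher | Pooled uncorrected | CMH |
|---|---|---|---|
| 0 | 0.78 | 0.80 | 0.80 |
| 0.5 | 0.75 | 0.77 | 0.79 |
| 1.0 | 0.66 | 0.69 | 0.75 |

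Pooled against CMH isolates center; Fisher against pooled shows Fisher's discreteness. Over 45 v 20, 40 v 15 and 30 v 10, with equal and unequal centers, the part due to center is 0.0–0.4, 1.1–1.7 and 4.6–5.6 points at SD 0, 0.5 and 1.0. Discreteness accounts for a further 1.0–3.5 points. At 60 v 10 and 75 v 5 every power is at least 0.999.

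**The case against.** Five replies deserve weight.

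- **No decision depends on it.** Success is Fisher p < 0.05. The per-protocol and hot-deck analyses repeat the Fisher test and are unaffected. The logistic model has no threshold, and a standard error in the thousands would alert any statistician. All of this stands, and it keeps the priority low.
- **The trigger may not occur.** Response is a one-grade change on a live-rated four-point scale, and rating variability alone can produce a control responder. One is enough to restore the fit. The documents give no control rate, and the 69% and 47% figures need true rates of 1–2%. This also stands, and is why a range is shown.
- **Table A 20 names no fitting method.** Maximum likelihood is the ordinary reading, but it is an inference. A Firth fit could fill the same columns, with Wald p = 0.0002 for 83/111 v 0/37 and 0.02 for 30/111 v 0/37. The method gap is therefore the core of the point. However, 0.02 beside a Fisher p of 8e-5 shows that the Wald column still understates the evidence after penalization.
- **Center is a preference.** Fisher is valid, and the gain is nil at large effects, which the documents suggest: the treatment target is at least one grade, and the only chin figure is 77.8% at 18 months, for a related filler on another scale. This rules out changing the primary test. It does not explain why the one adjusted model omits the stratification factor.
- **Redactions.** Protocol 10.4 has blacked-out gaps and SAP 2.4.2 ends in one, so hidden text on the model or on center cannot be excluded. SAP 2.4.3 and Table A 20 show no redaction.

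**Conclusion.** Both points hold, at low priority.

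The failure with zero control responders is a mathematical property of the fit and needs no assumption beyond maximum likelihood. How likely it is rests on the assumed control rate: substantial at 1–5% and small from 10% upward. The baseline splits, treated counts and center allocation in the examples are illustrative.

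Omitting center is not an error in the decision rule. Fisher is conservative, clearly so when centers differ strongly. The cost is power, and only if centers differ and the effect is moderate; the between-center SD and center sizes are assumptions.

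The primary result, the success rule and the sample size are untouched. What is at risk is a misleading treatment row in the analysis meant to show robustness, with no pre-specified replacement.

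**What to change.** Before database lock:

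1. Fit Table A 20 by Firth penalized likelihood with baseline GCRS, treatment and center. Report the odds ratio, the penalized likelihood-ratio p-value and the profile-likelihood 95% interval in place of the Wald chi-square. If the redacted part of protocol 10.4 names the logistic model, list this change in SAP 2.8, which now records none.
2. Optionally, add one sensitivity analysis of the Month 6 primary endpoint (FAS, BOCF): a Cochran-Mantel-Haenszel test stratified by center, with a Mantel-Haenszel 95% interval for the difference. For 83/111 v 0/37 the difference is 0.75 (0.67 to 0.83).

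Keep Fisher as the primary test and success rule, and for the earlier time points in SAP 2.4.4.

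The cost is SAP wording, one extra analysis and a less familiar fit. With no control responder the upper Firth limit is uninformative (odds ratio 28 to 27,000 for 83/111 v 0/37), so only the lower limit should be interpreted. The CMH test is asymptotic: simulated size was 2.0–5.1% (Fisher 0.4–3.9% over the same null rates of 1–40%), and coverage of the Mantel-Haenszel interval was 93.3–95.4%. That is adequate for a sensitivity analysis.
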